3.3.2 Derivation of Primed vaccine group

For Supplemental Cohort 1 and Cohort 2 booster arms:

- Actual prior COVID-19 vaccination history reported in eCRF will be used to derive the prior primed COVID-19 vaccine group for each participant.
- In case there will be mixed prior primed COVID-19 vaccine regimen, below derivation rule will be applied for each population analysis set:

Analysis set	Individual primed COVID-19 vaccine classification	Pooled platform classification	Consideration
PPAS	Not included in PPAS	Not included in PPAS	Violate IE, exclude from PPAS
FAS	Derived as first dose of primed COVID-19 vaccine	Derived as pooled primed platform	If primed COVID-19 vaccines belong to the same platform
CMIAS	Not included in CMIAS	Not included in CMIAS	Violate IE, exclude from CMIAS
VTAS	Not included in VTAS	Not included in VTAS	Violate IE, exclude from VTAS
SafAS	Derived as first dose of primed COVID-19 vaccine	Derived as pooled primed platform	If primed COVID-19 vaccines belong to the same platform

3.4 Statistical Analyses

The SAP will be finalized prior to the database lock for any interim analysis applicable to the Supplemental Cohorts 1 and 2. Additional SAP amendments may be performed after execution of interim analysis and before the database lock for any additional analysis occurring in between any such interim analyses and the final analysis.

3.4.1 General Considerations

The statistical analyses will be performed under the responsibility of the Sponsor's Biostatistics platform using SAS® Version 9.4 or later.

For descriptive purposes, the following statistics will be presented:

Table 3.3: Descriptive statistics produced

Disposition and follow-up description	Categorical data	At least number of subjects (Percentage of subjects are also possible).
	Continuous data	Mean, standard deviation, quartiles, minimum and maximum.
Baseline characteristics	Categorical data	Number of subjects. Percentage of subjects.
	Continuous data	Mean, standard deviation, quartiles, minimum and maximum.
Clinical safety results	Categorical data	Solicited: Number and percentage (95% CIs) of subjects. Unsolicited: Number and percentage (95% CIs) of subjects and number of events.
Immunogenicity results	Categorical data (seroresponse, fold-rise)	Number and percentage (95% CIs) of subjects.
	Continuous data (titer / data)	Anti-Log10 (work on Log10 distribution, and anti-Log10 applied): Geometric mean, 95% CI of the geometric mean. Graphical representation by Reverse Cumulative Distribution Curve (RCDC).

The CI for the single proportion will be calculated using the exact binomial method (Clopper-Pearson method, quoted by Newcombe (1), ie, using the inverse of the beta integral with SAS®).

For immunogenicity results, assuming that Log10 transformation of the titers / data follows a normal distribution, at first, the mean and the 95% CI will be calculated on Log10 (titers / data) using the usual calculation for normal distribution (using Student's t distribution with n-1 degree of freedom), then anti-log transformations will be applied to the results of calculations, in order to provide geometric means (GMs) and their 95% CI.

3.4.2 Primary Endpoints - Immunogenicity

Due to the nature of immunogenicity titer, logarithm transformation of the individual data (titers or concentrations) ($\log_{10}(\text{data})$) will be calculated and assumed to be normally distributed.

The statistical inference will be based on the use of the two-sided 98.3% CI (Supplemental Cohorts 1 and 2) for non-inferiority of difference in means of post-vaccination log10 transformed concentrations between the 2 groups with normal approximation.

Confidence interval for the GMT ratio between booster arms and comparator group for Supplemental Cohorts 1 and 2 – Welch's t-interval

The details about the calculations of the CI for the GMT ratio between 2 groups are as follows:

Logarithmic transformation of the individual titers will be calculated first. Assuming that individual \log_{10} (titer) is normally distributed, the 98.3% CI (Supplemental Cohorts 1 and 2) for

the difference in \log_{10} (GMT) between group i and group j will be in the form:

$$\bar{X}_i - \bar{X}_j \pm t(\alpha/2, r) \cdot \sqrt{S^2_{\bar{X}_i}/n_i + S^2_{\bar{X}_j}/n_j}$$

where $\bar{X}_i = \log_{10}(\text{GMT})$ is the sample mean of $\log_{10}(\text{titer})$ of Group i, n_i and S_i^2 are the sample size

and sample variance of Group i, $\bar{X}_j = \log_{10}(\text{GMT})$ is the sample mean of $\log_{10}(\text{titer})$ of Group j, n_j and S_j^2 are the sample size and sample variance of Group j,

where the r degrees of freedom are approximated by:

$$r = \frac{\left(\frac{S^2_{\bar{X}_i}}{n_i} + \frac{S^2_{\bar{X}_j}}{n_j}\right)^2}{\frac{(S^2_{\bar{X}_i}/n_i)^2}{n_i - 1} + \frac{(S^2_{\bar{X}_j}/n_j)^2}{n_j - 1}}$$

take the integer portion of r, that is, use $[r]$, $t(1-\alpha/2, [r])$ is the 100(1- $\alpha/2$) percentile of the t -distribution with degrees of freedom $[r]$.

The margin used for non-inferiority hypothesis testing are $1/1.5=0.667$ for GMTs. The non-inferiority in terms of GMTs will be demonstrated, if the lower limit of the 2-sided 98.3% CI (Supplemental Cohorts 1 and 2) for the difference of \log_{10} (GMT) of tested vaccine candidate arm and \log_{10} (GMT) of the control arm $> \log_{10}(1/1.5)$.

For the geometric mean of individual titer ratios post-boost versus pre-boost for superiority testing, the two-sided 98.3% CI (Supplemental Cohorts 1 and 2) of post-booster versus pre-booster will be calculated using \log_{10} -transformed titers assume normal distribution.

Confidence interval for the paired GMTR

The Geometric mean of titer ratio is defined as:

$$GMTR = \left(\prod_{i=1}^n ratio_i \right)^{\frac{1}{n}} = 10^{\frac{\sum_{i=1}^n \log_{10}(ratio_i)}{n}} = 10^{\frac{\sum_{i=1}^n \log_{10}\left(\frac{post_i}{pre_i}\right)}{n}}$$

The normal approximation will be used to calculate the 2-sided 98.3% CIs for the individual group GMTRs as follows:

$$10^{(\bar{x} \pm t_{n-1, \alpha/2} \sqrt{v(\bar{x})})}$$

where $10^{(\bar{x})}$ is the GMTR, $\bar{x} = \frac{1}{N} \sum \log_{10}(x)$, $\log_{10}(x)$ is the log base 10 of the titer ratio (post/pre), N is the number of subjects with non-missing value for pre and post-vaccination,

$\sqrt{V(\bar{x})}$ is the estimated standard deviation of \bar{x} , and $t_{n-1, \alpha/2}$ is the 100(1- $\alpha/2$) percentile of the central t -distribution with $n-1$ degrees of freedom.

The margin used for superiority hypothesis testing are 2 for individual group GMTRs. The superiority in terms of GMTRs will be demonstrated if the lower limit of the 2-sided 98.3% CI (Supplemental Cohorts 1 and 2) for the mean of \log_{10} (GMTRs) $> \log_{10}(2)$.

GMTs in each injection group and GMT ratios between injection groups will be descriptively summarized along with their 95% CIs using the normal approximation of log-transformed titers. GMTs will be presented in original scale that are re-converted from log-transformed titers. The 95% CI of GMT ratios between booster arms and comparator group will base on the Welch's t-interval for Supplemental Cohort 1 and 2 will base on the Student t-distribution.

Analyses will be performed for both FAS and PPAS, but the conclusion will be made mainly from results based on PPAS and supported by results based on FAS.

Subgroup analyses, where applicable, will be performed by age-group (18-55 years and ≥ 56 years) for intervention groups, by priming vaccine (Supplemental Cohorts 1 and 2), and by priming platform (Supplemental Cohorts 1 and 2), in addition to the Overall group.

3.4.3 Primary Endpoints - Safety

The main parameter will be described for all safety endpoints. The percentage of participants (using as denominator the number of participants) will be provided for analysis of solicited AEs, unsolicited AEs (including immediate systemic AEs within 30 minutes), SAEs, AESIs and MAAEs. The corresponding 95% CIs for the percentages will be calculated based on the Clopper--Pearson method. In the priming vaccine groups (comparator for Cohorts 1 and 2), subgroup analyses will be performed by age group (18-55 years and ≥ 56 years), high-risk medical conditions group, and baseline SARS-CoV-2 Naïve status for main safety analyses. In the booster vaccine groups (in Cohorts 1 and 2), subgroup analyses will be performed by age group (18-55 years and ≥ 56 years), high-risk medical conditions group, priming vaccine platform and individual priming vaccine. Safety endpoints will be analyzed for each of the CoV2 preS dTM primary series dosage administered in the original Phase II cohort (ie, 5-10-15 μ g) for Cohort 2.

Safety endpoints that occurred after authorized/approved COVID-19 vaccine injection will be listed separately.

SafAS population will be used for safety analyses for the following endpoints:

- Presence, and relationship of unsolicited (immediate) systemic AEs reported in the 30 minutes after each vaccination.
- Presence, time of onset, number of days of occurrence, intensity, action taken, and whether the reaction led to early termination from the study, of solicited (pre-listed in the participant's DC and CRF) injection site reactions and systemic reactions occurring up to 7 days after each vaccination.
- Presence, nature (Medical Dictionary for Regulatory Activities [MedDRA] system organ class [SOC] and preferred term [PT]), time of onset, duration, intensity, relationship to

vaccination and whether the event led to early termination from the study of unsolicited AEs reported up to 21 days after the last vaccination.

- Presence, nature (MedDRA SOC and PT), time of onset, seriousness criteria, relationship to vaccination, outcome, and whether the event led to early termination from the study, of SAEs.
- Presence, seriousness, intensity, nature (MedDRA SOC and PT), time of onset, duration, relationship to vaccination of all protocol-specified AESIs from the time of the first study vaccination throughout the study.
- Presence, seriousness, intensity, nature (MedDRA SOC and PT), time of onset, duration, relationship to vaccination of MAAEs throughout the study.

Confidence interval for the single proportion of AEs

The exact 2-sided 95% CI for the single proportion will be constructed using Clopper-Pearson's method, quoted by Newcombe where:

Lower bound: $1 - Beta(1 - \alpha / 2, n - r + 1, r)$ and

Upper bound: $Beta(1 - \alpha / 2, r + 1, n - r)$

where $\alpha=0.05$, and r is the observed number of events/responders in n observations.

3.4.4 Secondary Endpoints - Immunogenicity

For Supplemental Cohorts 1 and 2 conditional secondary objectives on non-inferiority claim of post-booster versus post-primary vaccination, the statistical inference will be based on the use of the two-sided 98.3% CI of difference in geometric means of post-vaccination \log_{10} transformed titer values between the 2 groups with normal approximation.

The margin used for non-inferiority hypothesis testing are $1/1.5=0.667$ for GMTs. The non-inferiority in terms of GMTs will be demonstrated if the lower limit of the 2-sided 98.3% CI (Supplemental Cohorts 1 and 2) for the difference of \log_{10} (GMT) of tested vaccine candidate arm and \log_{10} (GMT) of the control arm $> \log_{10}(1/1.5)$.

For Supplemental Cohorts 1 and 2 conditional secondary objectives on superiority claim of post-booster versus pre-booster, the two-sided 98.3% CI of post-booster versus pre-booster will be calculated using \log_{10} -transformed titers assuming a normal distribution.

The margin used for superiority hypothesis testing on post-booster versus pre-booster responses in Supplemental Cohorts 1 and 2 on individual group GMTRs is 2. The superiority in terms of GMTRs will be demonstrated if the lower limit of the 2-sided 98.3% CI (Supplemental Cohorts 1 and 2) of \log_{10} (GMTRs) $> \log_{10}(2)$.

For Supplemental Cohort 2 conditional secondary objective on superiority claim of B.1.351 for post-booster versus post-primary vaccination, the two-sided 98.3% CI of post-booster versus post-primary will be based on the use of the two-sided 98.3% CI of difference in geometric means of post-vaccination \log_{10} transformed titer values between the 2 groups with normal approximation.

The margin used for superiority hypothesis testing on post-booster versus post-primary responses to B.1.351 in Supplemental Cohort 2 on individual group GMTRs is 1.5. The superiority in terms

of GMTRs will be demonstrated, if the lower limit of the 2-sided 98.3% CI (Supplemental Cohorts 1 and 2) of $\log_{10}(\text{GMTRs}) > \log_{10}(1.5)$.

For Supplemental Cohorts 1 and 2 conditional secondary objectives on non-inferiority claim of seroresponse, the two-sided 98.3% CI difference in proportions between groups will be computed using the Wilson score method without continuity correction.

The margin used for non-inferiority hypothesis testing is -10% for seroresponse rate. The non-inferiority in terms of seroresponse rates will be demonstrated if the lower limit of the 2-sided 98.3% CI for the difference of seroresponse rates > -0.1 .

Confidence interval for the difference in proportions between two groups

For the non-inferiority hypotheses in terms of seroresponse rate, the two-sided 95% CI difference in proportions between groups will be computed using the Wilson score method without continuity correction (2) as follows:

Let $\hat{\theta} = \pi_A - \pi_B$, then if $L = \hat{\theta} - \delta$ and $U = \hat{\theta} + \varepsilon$ are respectively the lower and the upper limits of the CI, where:

$$\delta = Z_{\alpha/2} \sqrt{\left\{ \frac{l_1(1-l_1)}{n_1} + \frac{u_2(1-u_2)}{n_2} \right\}}$$

$$\varepsilon = Z_{\alpha/2} \sqrt{\left\{ \frac{l_2(1-l_2)}{n_2} + \frac{u_1(1-u_1)}{n_1} \right\}}$$

l_1 and u_1 are calculated from the CI of the single proportion in Group A given by:

$$\frac{(2n_1 p_1 + Z_{\alpha/2}^2 \pm Z_{\alpha/2} \sqrt{(Z_{\alpha/2}^2 + 4n_1 p_1(1-p_1))})}{2(n_1 + Z_{\alpha/2}^2)}$$

l_2 and u_2 are calculated from the CI of the single proportion in Group B given by:

$$\frac{(2n_2 p_2 + Z_{\alpha/2}^2 \pm Z_{\alpha/2} \sqrt{(Z_{\alpha/2}^2 + 4n_2 p_2(1-p_2))})}{2(n_2 + Z_{\alpha/2}^2)}$$

where $Z_{\alpha/2}$ is the upper $(1-\alpha/2)$ th percentile of the standard normal distribution.

The margin used for non-inferiority hypothesis testing is -10% for seroresponse rate. The non-inferiority in terms of seroresponse rates will be demonstrated if the lower limit of the 2-sided 95% CI for the difference of seroresponse rates > -0.1 .

The percentage of responders and participants having 2-fold rise (2FR), 4-fold rise (4FR) will be provided against each endpoint with the corresponding 95% CIs using the Clopper-Pearson method. FR defined as fold-rise from post-vaccination relative to pre-vaccination, the pre-vaccination could be the D01 at Phase III study or D01 at Phase II study for CoV2 preS dTM-

AS03 primed participants. Differences of percentages of responders and participants with 2FR, 4FR will be provided with 95% CI calculated by Newcombe-Wilson score method without continuity correction.

Confidence interval for the single proportion

The exact 2-sided 95% CI for the single proportion will be constructed using Clopper-Pearson's method, quoted by Newcombe where:

Lower bound: $1 - Beta(1 - \alpha / 2, n - r + 1, r)$ and

Upper bound: $Beta(1 - \alpha / 2, r + 1, n - r)$

where r is the observed number of events/responders in n observations.

GMTs or GMCs in each injection group and GMT or GMC ratios between injection groups will be descriptively summarized along with their 95% CIs using the normal approximation of log-transformed titers. GMTs or GMCs will be presented in original scale that are re-converted from log-transformed titers. The 95% CI of GMT or GMC ratios between booster arms and comparator group will base on the Welch's t-interval for Supplemental Cohort 1 and 2.

The 95% CI of GMT ratios after booster dose at D15 between booster arms based on the Student t-distribution and 95% CI of difference on seroresponse rate at D15 relative to D01 between booster arms based on the Newcombe-Wilson score method without continuity correction will be provided for homogeneity/comparability evaluation on booster effect across different primary series vaccines, by age group and overall.

GMTRs or GMCRs is defined as ratio of individual geometric mean titer or concentration for each injection group (post-vaccination/pre-vaccination for each injection). GMTR or GMCR will be summarized with 95% CI (Normal approximation). Additional parameters may be displayed as appropriate.

Confidence interval for the individual group GMT or GMC and GMTR or GMCR

The normal approximation will be used to calculate the 2-sided 95% CIs for the individual group GMT or GMC and GMTRs or GMCRs as follows:

$$10^{(\bar{x} \pm t_{n-1, \alpha/2} \sqrt{v(\bar{x})})}$$

where $10^{(\bar{x})}$ is the GMT or GMC, $\bar{x} = \frac{1}{N} \sum \log_{10}(x)$, $\log_{10}(x)$ is the log base 10 of the observed titer or concentration, N is the total observation in each injection group, $\sqrt{V(\bar{x})}$ is the estimated standard deviation of \bar{x} , and $t_{n-1, \alpha/2}$ is the 100(1- $\alpha/2$) percentile of the central t -distribution with $n-1$ degrees of freedom.

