For participants, 18-55 years of age, primed with the Pfizer/BioNTech vaccine, 14 days after the booster dose (ie, D15) of CoV2 preS dTM-AS03 (B.1.351) (non-exploratory arm only) or CoV2 preS dTM-AS03 (D614 + B.1.351), GMT against B.1.351 of CoV2 preS dTM-AS03 (B.1.351) or/and CoV2 preS dTM-AS03 (D614 + B.1.351) is superior to the GMT against B.1.351 of the primary vaccination Comparator Group.

Null hypothesis (H_0) : $\text{GMT}_{(\text{variant})} / \text{GMT}_{(\text{comparator})} \leq 1.5$

Alternative hypothesis (H_1) : $\text{GMT}_{(\text{variant})} / \text{GMT}_{(\text{comparator})} > 1.5$

Each of the 2 variant-containing vaccine groups, CoV2 preS dTM-AS03 (B.1.351) or CoV2 preS dTM-AS03 (D614 + B.1.351), will be tested separately. The superiority will be demonstrated if the lower limit of the two-sided 98.3% CI of the ratio of the GMT is greater than 1.5 for each or both variant-containing vaccine group(s).

If the primary immunogenicity objective in participants primed with the Pfizer/BioNTech vaccine, conditional secondary immunogenicity objective in participants primed with an mRNA vaccine, and conditional secondary immunogenicity objective on GMT in participants primed with the Pfizer/BioNTech vaccine are all achieved. Conditional secondary immunogenicity

objective on seroresponse for participants primed with the Pfizer/BioNTech vaccine and an mRNA vaccine will be tested sequentially.

Conditional secondary objective 3: non-inferiority in terms of seroresponse rate for participants primed with the Pfizer/BioNTech or mRNA vaccines:

For participants, 18-55 years old, primed with the Pfizer/BioNTech vaccine or an mRNA vaccine , 14 days after the booster dose (ie, D15) with CoV2 preS dTM-AS03 (B.1.351) or CoV2 preS dTM-AS03 (D614 + B.1.351) and 14 days after the second dose (ie, D36) of the Comparator Group, the seroresponse rate against D614G (if the SARS-CoV-2 D614G variant remains in circulation globally based on reports from authorities [eg, WHO]) and B.1.351 of the Booster Group CoV2 preS dTM-AS03 (D614), is non-inferior to the seroresponse rate against D614G of the Comparator Group.

Null hypothesis (H0) : $p_{(\text{booster})} - p_{(\text{comparator})} \leq -10\%$

Alternative hypothesis (H1) : $p_{(\text{booster})} - p_{(\text{comparator})} > -10\%$

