3.2 Sample Size Determination

3.2.1 Supplemental Phase III Cohorts 1 and 2

A Bonferroni adjustment is used to control the overall type I error rate at 0.025 one-sided in Supplemental Cohorts 1 and 2, so each comparison of the Booster Group with the Comparator Group will be performed at one-sided significance level of 0.00833 (0.025/3). No alpha-splitting within hypothesis testing of co-primary endpoints. Assumed attrition rate of Primary Vaccination Group is 10% and Booster Group is 3% (it is anticipated that attrition to 14 days post booster will be limited and smaller than the attrition to D36 in the Comparator Group). Other assumptions for sample size calculation are as follows:

- The PsVN Std Dev is around 0.65 for primary vaccination at D36 and around 1.0 for booster vaccination at D22 on \log_{10} scale base on immunogenicity data obtained from Monogram for the corresponding assay
 - Note: The assumption of the standard deviation of the assay is based on the final interim data of D614G on the PPAS Naïve-D01+D22 at D36 and FAS NonNaïveD01 at D22 from VAT0002 Original Phase II Cohort in participants 18-55 years of age.
- For the primary and secondary objectives in terms of GMT non-inferiority against the comparator (using the D614G titers elicited by the comparator as the benchmark), the ratio of group GMT margin is 1/1.5, the assumed true ratio of group GMT for D614 containing vaccines (comparing D614G titers in both booster vaccine and priming comparator) is 1.5 (this is informed by preliminary interim data from VAT0002 Original Phase II Cohort, indicating titers generally higher in the non-naïve individuals after a single dose, compared to the titers in naïve individuals after 2 doses); and the assumed true ratio of group GMT for the B1.351 variant-containing vaccines (comparing B.1.351 titers in variant-containing vaccines versus D614G titers in the comparator D614 vaccine) is 1 (this is assumed in the absence of data).

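### Section 3.4.4 puts the success rule for B.1.351 superiority over the Comparator on a within-arm post/pre ratio, contradicting the between-group rule in Section 3.1.1.3

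*SAP*

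**What the plan says.** Section 3.1.1.3 (Cohort 2, conditional secondary objective 2; numbered 3 in Table 2.1) concerns Pfizer/BioNTech-primed adults aged 18-55. The D15 GMT against B.1.351 in a variant-containing booster group "is superior to the GMT against B.1.351 of the primary vaccination Comparator Group". The null hypothesis is a booster/Comparator GMT ratio of at most 1.5. Success requires the lower limit of the two-sided 98.3% CI of that GMT ratio to exceed 1.5.

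Section 3.4.4 returns to this objective in two consecutive paragraphs. The first describes the interval: "the two-sided 98.3% CI of post-booster versus post-primary will be based on the use of the two-sided 98.3% CI of difference in geometric means", taken between the two groups. The second gives the decision rule: "The margin used for superiority hypothesis testing on post-booster versus post-primary responses to B.1.351 in Supplemental Cohort 2 on individual group GMTRs is 1.5". Superiority is then declared when the lower 98.3% limit of log10(GMTRs) exceeds log10(1.5). Apart from a comma and the bound, this success sentence matches the one for the post-booster versus pre-booster test with margin 2: "of GMTRs will be demonstrated if the lower limit of the 2-sided 98.3% CI (Supplemental Cohorts 1 and 2) of" log10(GMTRs).

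The same section defines the term: "GMTRs or GMCRs is defined as ratio of individual geometric mean titer or concentration for each injection group (post-vaccination/pre-vaccination for each injection". Section 3.4.2 gives its formula, the geometric mean of each participant's post/pre ratio, with a one-sample t interval on n-1 degrees of freedom.

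**The concern.** The margin and success sentences in Section 3.4.4 attach the between-group claim to a quantity that the SAP defines, with a formula, as a within-arm ratio. The SAP knows the difference: the non-inferiority rule in the same section is written on the difference between the log10 GMTs of the candidate and control arms. One confirmatory claim therefore has two incompatible success rules, and the wrong one is in the analysis-methods section, next to a ready-made formula.

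This is the SAP's only hypothesis-tested claim that a variant-containing booster is superior to the Comparator against B.1.351. Under Section 3.1.1 it also gates the seroresponse tests for both Cohort 2 booster candidates. An analysis that took the two sentences at face value would report superiority to the Comparator without using the Comparator's data, and would open that gate with no test behind it.

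**Working it through.** **Inputs**
- One-sided alpha 0.025/3 = 0.00833 (Section 3.2.1); normal quantile 2.394.
- Evaluable numbers: booster 515 × 0.97 ≈ 499; Comparator 515 × 0.90 ≈ 463 (Section 3.2.1).
- SD on the log10 scale: booster 1.0, Comparator 0.65 (Table 3.1); post/pre difference 1.0 (Section 3.2.1).
- Between-group superiority: margin 1.5, assumed true ratio 3. Post/pre: margin 2, assumed true ratio 5 (Section 3.2.1).

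**1. Reproducing the plan's power with the between-group test**

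SE = √(1.0²/499 + 0.65²/463) = 0.0540.

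Noncentrality = log10(3/1.5)/0.0540 = 0.3010/0.0540 = 5.57.

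The Welch (noncentral t) power is 99.92%, or 99.96% without attrition. The normal approximation, Φ(5.57 − 2.394), gives 99.93%. Table 3.1 states more than 99.9%, so the figure reproduces. As a check on n and SD, the same SE gives 80.5% for the B.1.351 non-inferiority test at a true ratio of 1, as Table 3.1 states.

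The power figure alone does not settle which rule is meant: a paired test of a true fold-rise of 5 against 1.5 also has power above 99.9%. What identifies the test is the set of inputs in Table 3.1, a ratio of group GMTs with a Comparator SD.

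**2. The literal Section 3.4.4 rule**

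Primary objective 2 (Section 3.1.1.3) requires, in the same arms and against the same strain, that the lower 98.3% limit of the post/pre ratio exceed 2. The literal rule asks whether that same limit exceeds 1.5. Since log10(2) = 0.301 and log10(1.5) = 0.176, the first implies the second. This is logic and needs no assumption about the data.

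In terms of observed estimates (normal approximation):
- Paired half-width = 2.394 × 1.0/√499 = 0.107, a factor of 10^0.107 = 1.28. Primary objective 2 needs an observed fold-rise of about 2 × 1.28 = 2.56; the literal rule needs only 1.5 × 1.28 = 1.92.
- Between-group half-width = 2.394 × 0.0540 = 0.129, a factor of 1.35. The Section 3.1.1.3 rule needs an observed booster/Comparator ratio of about 1.5 × 1.347 = 2.02.

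**3. How far the two rules diverge**

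Simulation: 10,000 trials per row, n = 499 and 463, true fold-rise 5. The pre/post correlation is taken as 0.5, an assumption that makes the difference SD 1.0 when the pre and post SDs are each 1.0.

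| True booster/Comparator ratio | Between-group rule passes | Literal GMTR rule passes |
|---|---|---|
| 1.0 | 0% | 100% |
| 1.5 (null boundary) | 0.91% (nominal 0.83%) | 100% |

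No trial met primary objective 2 and failed the literal rule. The between-group test has 46.6% power at a true ratio of 2. The SAP says its assumed ratio of 3 is made in the absence of data, so values at which the two rules disagree are not remote.

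**The case against.** A reader might infer that the plan drops the Comparator from this claim, so that superiority is met automatically once the primary objectives are met. The documents do not support that:
- The disputed margin sentence itself says post-booster versus post-primary. A within-arm ratio would be post-booster versus pre-booster, the phrase Section 3.4.4 uses for the margin-2 test.
- The paragraph before it fixes the CI for this objective as a difference between the two groups.
- Section 3.1.1.3 gives both the hypothesis and a complete, correct success rule on the GMT ratio.
- Table 2.1 lists only the booster D15 and Comparator D36 titers against B.1.351 as endpoints for this objective. It lists no D01 titer, so a post/pre ratio cannot be formed from them.
- Table 3.1 powers a ratio of group GMTs, with a Comparator SD of 0.65.

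All of this stands. It shows what is intended and which text to correct. It also means that the 100% versus 0.9% contrast describes literal programming of two sentences, not the operating characteristics of the plan as a whole. It does not remove the contradiction: *individual group GMTRs* is a defined term here, and it appears in both the margin and the success sentence of a confirmatory test.

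**Conclusion.** The concern holds as a mis-specified decision parameter. The Section 3.4.4 rule for B.1.351 superiority names a within-arm post/pre ratio and contradicts Section 3.1.1.3, its own preceding paragraph, Table 2.1 and Table 3.1.

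If the between-group test is run, as the rest of the SAP shows is intended, nothing changes: power is about 99.9% at a true ratio of 3, with 0.83% one-sided error at the margin. If the two sentences were programmed literally, the test would duplicate a weaker form of primary objective 2 and say nothing about the Comparator. The redundancy rests only on the two thresholds being applied to the same confidence limit. The simulated pass rates also rest on the SAP's SDs, attrition and fold-rise of 5, and on the assumed correlation of 0.5.

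**What to change.** Replace the two decision sentences in Section 3.4.4 with text to this effect: the margin for superiority of booster D15 over Comparator D36 responses to B.1.351 is 1.5 on the between-group GMT ratio; superiority is demonstrated if the lower limit of the two-sided 98.3% Welch CI for log10(GMT booster D15, B.1.351) minus log10(GMT Comparator D36, B.1.351) exceeds log10(1.5). Reserve GMTR for paired post/pre ratios throughout.

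The cost is two sentences of SAP text, best changed before the database lock at which this claim is tested. The Welch interval is already specified in Section 3.4.2. No new data are needed, and alpha, sample size and stated power stay as they are.
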